Appendix 1 Schedule of Assessments: Table A (cont.)

- 6 **Informed Consent** will be obtained in written form from all patients at screening in order to meet eligibility for the study.
- 7 **Vital signs** will be obtained while the patient is in the semi supine position (after 5 minutes), i.e., pulse rate, systolic, and diastolic blood pressure, respiration rate, and temperature. On OCR infusion visits, the vital signs should be taken within 45 minutes prior to the methylprednisolone infusion in all patients. In addition, vital signs should be obtained prior to the study drug infusion, then every 15 minutes (\pm 5 minutes) for the first hour; then every 30 minutes (\pm 10 minutes) until 1 hour after the end of the infusion. On immunization days, vital signs should be taken prior to immunization. On non-infusion/non-immunization days, the vital signs may be taken at any time during the visit.
- 8 **ECG (pre- and post-dose):** On infusion visits, ECG should be taken within 45 minutes prior to the methylprednisolone infusion in all patients, and within 60 minutes after completion of the OCR infusion. On non-infusion days, the ECG may be taken at any time during the visit.
- 9 Weight should be obtained prior to the OCR infusion.
- 10 The EDSS should be obtained at baseline (pre-dose). An EDSS should also be performed if PML is suspected
- 11 MRI should be done at Baseline and annually throughout the OOE period (\pm 4-week window) as per Section 4.7.8.5. The annual MRIs in the OOE should be carried out as close as possible within a year of the baseline MRI performed at study entry. It can be performed at an unscheduled visit or be carried out at a scheduled visit, e.g., at the visit scheduled 2 weeks prior to the next OCR infusion (Visit q22), where retreatment criteria are assessed. Please note: at the withdrawal from Immunization Period or OOE Period, an MRI scan will be required only if not performed in the prior 4 weeks.
- 12 After informed consent, but prior to initiation of study medications, only SAEs caused by a protocol-mandated intervention will be collected (e.g., SAEs related to invasive procedures such as biopsies, medication washout, or no treatment run-in).
- 13 **Telephone interview:** The telephone interview will be conducted by site personnel familiar with the patient(s) every 4 weeks (\pm 3 days) between the study visits throughout all periods and the SFU until 48 weeks after the last infusion of OCR. The telephone interview is done to identify and collect information on any changes in the patient's health status that warrant an unscheduled visit. See [Appendix 2](#) for the semi-structured telephone interview.
- 14 **Pregnancy test:** Serum β -hCG must be performed at screening in women of childbearing potential. Subsequently, urine β -hCG [sensitivity of at least 25 mIU/mL] will be done. On infusion and immunization visits, the urine pregnancy test should be performed prior to methylprednisolone infusion in all women of child-bearing potential. If positive, do not dose and confirm with a serum pregnancy test.
- 15 **ADA:** On infusion visits, samples are collected prior to the methylprednisolone infusion.
- 16 **PK samples:** On infusion visits, a blood sample should be taken before the methylprednisolone infusion and on infusion visits at Weeks 1, 2, and 24 an additional sample within 30 minutes after the end of the OCR infusion. At other times (non-infusion visits), samples may be taken at any time during the visit.
- 17 **FSH:** FSH only applicable to women to confirm the post-menopausal status at screening.
- 18 **Hepatitis screening:** to be eligible, all patients must have negative a negative HepCAb, a negative HBsAg result and either negative HBcAb or a positive HBcAb but negative HBV DNA.
- 19 **Hepatitis B virus DNA monitoring.** For those eligible patients enrolled with positive total HBcAb, HB virus DNA (PCR) must be repeated every 24 weeks.

Appendix 1 Schedule of Assessments: Table A (cont.)

- 20 **CD4 count:** will be measured separately at screening, and be included in the flow cytometry (FACS) panel at all following visits including every q22-week visit in order to inform eligibility/re-treatment criteria. Other re-treatment labs will be measured as part of IgG and routine safety labs (see item 21 and 22).
- 21 **Flow cytometry:** including CD19 and other circulating B-cell subsets, T-cells (including CD4 cells), NK cells and other leukocytes. On the infusion days, samples should be collected prior to infusion of methylprednisolone.
- 22 **Routine safety labs.** On infusion visits, all urine and blood samples should be collected prior to the infusion of methylprednisolone. At other times, samples may be taken at any time during the visit.
- 23 All patients will receive **prophylactic treatment** with 100 mg of methylprednisolone IV 30 minutes prior to, and an IV or oral antihistamine such as diphenhydramine 50 mg 30–60 minutes prior to OCR infusions. In patients where methylprednisolone is contraindicated, corresponding doses of other IV steroids (e.g., dexamethasone) may be used as premedication. It is also recommended that patients receive an analgesic/antipyretic such as acetaminophen/paracetamol (1 g), 30–60 minutes prior to OCR infusions.
- 24 **Study drug administration:** The investigator must review the clinical and laboratory re-treatment criteria prior to re-dosing patients with study drug at Day 168 (Week 24) and prior to any subsequent OCR infusion.
- 25 Influenza vaccine and post-vaccination assessment for Group A2 only. Influenza can be administered between Weeks 12–20. Post-vaccine assessments must be done after 4 weeks. For patients in Group A2 who are due to receive the influenza vaccine during their country-specific influenza vaccine blackout period, administration of the vaccine should be given prior to the start of this blackout period. Group A1 patients can receive the influenza vaccine at any time at the discretion of the investigator.
- 26 M=Sample to be taken prior to immunization on days when vaccines are administered. On infusion visits, all urine and blood samples should be collected prior to the infusion of methylprednisolone. At other times, samples may be taken at any time during the visit.
- 27 Group A1 only.
- 28 TT-containing adsorbed vaccine refers to the combined tetanus and diphtheria (Td/DT) or tetanus, diphtheria, and acellular pertussis (DTaP/Tdap) vaccines.

Appendix 1 Schedule of Assessments: Table B

TABLE B: SCHEDULE OF ASSESSMENTS FOR IMMUNIZATION STUDY PERIOD AND OPTIONAL OCRELIZUMAB TREATMENT PERIOD

		Group B												
	Screening ¹	Immunization Study Period				OOE ^{2,3}						WD from Treatment ⁴	Unscheduled ⁴	Delayed Dosing ⁵
		1	28 (±4 d)	56 (±4 d)	84 ¹ (±4 d)	84 ¹ (±4 d)	98 (±2 d)	238 (±4 d)	252 (±2 d)	q22w (±4 d) (-2 w prior to q24 w)	q24 w ³ (±2 w)			
Study Day (Unless Noted) Window	-28 to -1	1	28 (±4 d)	56 (±4 d)	84 ¹ (±4 d)	84 ¹ (±4 d)	98 (±2 d)	238 (±4 d)	252 (±2 d)	q22w (±4 d) (-2 w prior to q24 w)	q24 w ³ (±2 w)			
Week	-4 to -1	—	4	8	12	12	14	34	36	q22 w ³	q24 w ³			
↓ = OCR infusion						↓	↓		↓		↓			
Informed consent ⁶	x													
Medical history, MS history, prior and concomitant treatments	x													
Eligibility review	x	x				x			x		x			
Physical and neurological examination	x	x				x	x		x		x	x	x	x
Vital signs ⁷	x	x	x	x	x	x	x		x		x	x	x	x
12-lead ECG ⁸	x	x				x	x		x		x	x		
Height	x													

Appendix 1 Schedule of Assessments: Table B (cont.)

Group B														
	Screening ¹	Immunization Study Period				OOE ^{2,3}						WD from Treatment ⁴	Unscheduled ⁴	Delayed Dosing ⁵
Study Day (Unless Noted) Window	-28 to -1	1	28 (±4 d)	56 (±4 d)	84¹ (±4 d)	84¹ (±4 d)	98 (±2 d)	238 (±4 d)	252 (±2 d)	q22w (±4 d) (-2 w prior to q24 w)	q24 w³ (±2 w)			
Week	-4 to -1	—	4	8	12	12	14	34	36	q22 w³	q24 w³			
Weight ⁹	x					x			x		x	x		
EDSS ¹⁰		x												
MRI (once annually [±4 w]) ¹¹	x										x			
Adverse events	Only SAEs ¹²	x	x	x	x	x	x	x	x	x	x	x	x	x
Telephone interview						Every 4 weeks ¹³								
Concomitant treatments		x	x	x	x	x	x	x	x	x	x	x	x	x
Pregnancy test ¹⁴	x	x	x	x	x	x	x		x		x	x	x	x
ADA ¹⁵						x	x	x	x	x	x	x		
PK samples ¹⁶						x	x		x		x	x		
FSH ¹⁷	x													
Hepatitis screening ¹⁸	x													

Appendix 1 Schedule of Assessments: Table B (cont.)

		Group B												
	Screening ¹	Immunization Study Period				OOE ^{2,3}						WD from Treatment ⁴	Unscheduled ⁴	Delayed Dosing ⁵
Study Day (Unless Noted) Window	-28 to -1	1	28 (±4 d)	56 (±4 d)	84¹ (±4 d)	84¹ (±4 d)	98 (±2 d)	238 (±4 d)	252 (±2 d)	q22w (±4 d) (-2 w prior to q24 w)	q24 w³ (±2 w)			
Week	-4 to -1	—	4	8	12	12	14	34	36	q22 w³	q24 w³			
HBV DNA ¹⁹ monitoring		X			X	X		X	X	X		X		
RPR	X													
CD4 count ²⁰	X					X		X	X	X	X	X		
IgG subtype		X ²¹			X ²¹	X ²¹		X		X		X		
Total Ig, IgA, IgG, IgM	X	X	X	X	X	X		X		X		X		
Flow cytometry ²²		X			X	X	X	X	X	X	X	X		
Routine safety labs ²³	X	X	X	X	X	X	X	X	X	X	X	X	X	X
Pretreatment with IV methylprednisolone and an antihistamine ²⁴						X	X		X		X			X
IV OCR ²⁵						X	X		X		X			X

Appendix 1 Schedule of Assessments: Table B (cont.)

	Group B													
	Screening ¹	Immunization Study Period				OOE ^{2,3}						WD from Treatment ⁴	Unscheduled ⁴	Delayed Dosing ⁵
Study Day (Unless Noted) Window	-28 to -1	1	28 (±4 d)	56 (±4 d)	84¹ (±4 d)	84¹ (±4 d)	98 (±2 d)	238 (±4 d)	252 (±2 d)	q22w (±4 d) (-2 w prior to q24 w)	q24 w³ (±2 w)			
Week	-4 to -1	—	4	8	12	12	14	34	36	q22 w³	q24 w³			
Influenza ²⁶		M ²⁶ → Influenza → +4 weeks M												
KLH		I/M ²⁷	I/M ²⁷	I/M ²⁷	M	M ²⁷								
23-PPV			I/M ²⁷	M	M	M ²⁷								
TT-containing vaccine ²⁸		I/M ²⁷	M	M										

ADA=anti-drug antibodies; β-hCG=β-human chorionic gonadotropin; BL=baseline; CD4=cluster of differentiation; 13-PCV-23=Conjugate pneumococcal vaccine; ECG=electrocardiogram; eCRF=electronic case report form; EDSS=Expanded Disability Status Scale; FSH=follicle-stimulating hormone; I= immunization; IV=intravenous; KLH= Keyhole Limpet hemocyanin; M= measurement pre-immunization and/or post-baseline immunization assessment;; OOE=Optional Ocrelizumab Extension Period; PK=pharmacokinetic; 23-PPV= 23-valent polysaccharide pneumococcus vaccine; RPR=rapid plasma reagin; SAE=serious adverse event; TT: Tetanus toxoid-containing vaccine SC=subcutaneous; w=week.

- 1 The screening period can be extended to a total period of 8 weeks in cases when a laboratory blood test needs to be repeated for confirmation during the screening interval, if a live vaccine must be administered by the patient's physician, or for other relevant clinical, administrative, or operational reasons.
- 2 The Immunization Study Period will end at Day 84 (Week 12). Assessments shown under Immunization Study Period should be performed on all patients. Assessments indicated in the OOE column should only be done if the patient chooses and is eligible to receive OCR.
- 3 Patients can continue to receive OCR (600 mg, single infusion) at an interval of 24 weeks (minimum interval of 22 weeks).

Ocrelizumab—F. Hoffmann-La Roche Ltd

109/Protocol BN29739, Version 8

Appendix 1 Schedule of Assessments: Table B (cont.)

- 4 **Unscheduled Visit:** assessments performed at unscheduled (non-dosing) visits will depend on the clinical needs of the patient. Other tests/assessments may be done as appropriate.
- 5 A delayed dosing visit will be performed and recorded in the Delayed Dosing Visit eCRF form when dosing cannot be administered at the scheduled dosing visit. Other tests or assessments may be done as appropriate.
- 6 **Informed Consent** will be obtained in written form from all patients at screening in order to meet eligibility for the study.
- 7 **Vital signs** will be obtained while the patient is in the semi supine position (after 5 minutes), i.e., pulse rate, systolic, and diastolic blood pressure, respiration rate, and temperature. On OCR infusion visits, the vital signs should be taken within 45 minutes prior to the methylprednisolone infusion in all patients. In addition, vital signs should be obtained prior to the study drug infusion, then every 15 minutes (\pm 5 minutes) for the first hour; then every 30 minutes (\pm 10 minutes) until 1 hour after the end of the infusion. On immunization days, vital signs should be taken prior to immunization. On non-infusion/non-immunization days, the vital signs may be taken at any time during the visit.
- 8 **ECG (pre- and post-dose):** On infusion visits, ECG should be taken within 45 minutes prior to the methylprednisolone infusion in all patients, and within 60 minutes after completion of the OCR infusion. On non-infusion days, the ECG may be taken at any time during the visit.
- 9 Weight should be obtained prior to the OCR infusion.
- 10 The EDSS should be obtained at baseline (pre-dose). An EDSS should also be performed if PML is suspected.
- 11 MRI should be done at Baseline and annually throughout the OOE Period, (\pm 4-week window) as per Section 4.7.8.5. The annual MRIs in the OOE should be carried out as close as possible within a year of the baseline MRI performed at study entry. It can be performed at an unscheduled visit or be carried out at a scheduled visit, e.g., at the visit scheduled 2 weeks prior the next OCR infusion (Visit q22), where retreatment criteria are assessed. To reduce the burden of additional visits for Group B patients, the scheduling of the annual MRI can be adapted to the pre-infusion visit schedule starting from the first annual MRI after the baseline MRI. Please note: at the withdrawal from treatment visits, an MRI scan will be required only if not performed in the prior 4 weeks.
- 12 After informed consent, but prior to initiation of study medications, only SAEs caused by a protocol-mandated intervention will be collected (e.g., SAEs related to invasive procedures such as biopsies, medication washout, or no treatment run-in).
- 13 **Telephone interview:** A semi-structured telephone interview will be done on a 4-week (\pm 3 days) basis between visits from Week 5 to identify and collect information on any changes in the patient's health status that warrant an unscheduled visit. See [Appendix 2](#) for the semi-structured telephone interview.
- 14 **Pregnancy test:** Serum β -hCG must be performed at screening in women of childbearing potential. Subsequently, urine β -hCG [sensitivity of at least 25 mIU/mL] will be done. On infusion and immunization visits, the urine pregnancy test should be performed prior to methylprednisolone infusion in all women of child-bearing potential. If positive, do not dose and confirm with a serum pregnancy test.
- 15 **ADA:** On infusion visits, samples are collected prior to the methylprednisolone infusion.

Appendix 1 Schedule of Assessments: Table B (cont.)

- 16 **PK samples:** On infusion visits, a PK blood sample should be taken before the methylprednisolone infusion and on infusion visits at Weeks 12, 14, and 36 an additional sample within 30 minutes after the end of the OCR infusion. At other times (non-infusion visits), samples may be taken at any time during the visit.
- 17 **FSH:** FSH only applicable to women to confirm the post-menopausal status at screening.
- 18 **Hepatitis screening:** to be eligible, all patients must have negative a negative HepCAb, a negative HBsAg result and either negative HBcAb or a positive HBcAb but negative HBV DNA.
- 19 **Hepatitis B virus DNA monitoring.** For those eligible patients enrolled with positive total HBcAb, HB virus DNA (PCR) must be repeated every 24 weeks.
- 20 **CD4 count:** will be measured separately at screening, and be part of the flow cytometry (FACS) panel at all following visits, including every q22w visit in order to inform eligibility/re-treatment criteria. Other re-treatment labs will be measured as part of IgG and routine safety labs (see item 20).
- 21 **IgG subtypes:** sample to be taken prior to immunization and /or OCR infusion.
- 22 **Flow cytometry:** including CD19 and other circulating B-cell subsets, T-cells (including CD4 cells), NK cells and other leukocytes. On the infusion days, samples should be collected prior to infusion of methylprednisolone.
- 23 **Routine safety labs.** On infusion visits, all urine and blood samples should be collected prior to the infusion of methylprednisolone. At other times, samples may be taken at any time during the visit.
- 24 All patients will receive **prophylactic treatment** with 100 mg of methylprednisolone IV 30 minutes prior to, and an IV or oral antihistamine such as diphenhydramine 50 mg 30–60 minutes prior to OCR infusions. In patients where methylprednisolone is contraindicated, corresponding doses of other IV steroids (e.g., dexamethasone) may be used as premedication. It is also recommended that patients receive an analgesic/antipyretic such as acetaminophen/paracetamol (1 g) 30–60 minutes prior to OCR infusions.
- 25 **Study drug administration:** The investigator must review the clinical and laboratory re-treatment criteria prior to dosing patients with study drug at Day 84 (Week 12) and prior to every subsequent OCR infusion.
- 26 Influenza vaccine for Group B: Influenza can be administered between Weeks 1 and 12. For patients who need to receive the influenza vaccine after Week 12, the OCR infusion must be delayed. Post-vaccine assessments must be done after 4 weeks. For patients in Group B who are due to receive the influenza vaccine during their country-specific influenza vaccine blackout period, administration of the vaccine should be given prior to the start of this blackout period
- 27 M=Sample to be taken prior to immunization on days when vaccines are administered. On infusion visits, all urine and blood samples should be collected prior to the infusion of methylprednisolone. At other times, samples may be taken at any time during the visit.
- 28 TT-containing adsorbed vaccine refers to the combined tetanus and diphtheria (DT/Td) or tetanus, diphtheria, and acellular pertussis (DTaP/Tdap) vaccines.

Appendix 1 Schedule of Assessments: Table C

TABLE C: SCHEDULE OF ASSESSMENTS FOR SAFETY FOLLOW-UP PERIOD (ALL PATIENTS)

	Safety Follow-Up^{1,8}	End of Observation or withdrawal from Safety Follow-Up¹
Assessment	Visits every 12 weeks (± 7 days)	
Flow cytometry ²	x	x
Telephone follow-up ³	x	
Urine pregnancy test	x	x
Routine safety labs ⁴	x	x
Total Ig, IgA, IgG, IgM	x ⁵	x
ADA ⁶	x ⁵	x
IgG subtype	x ⁵	x
HBV DNA ⁷	x	x
Vital signs	x	x
Physical and neurological examination	x ⁵	x
Adverse events	x	x
Concomitant treatments	x	x

DNA=deoxyribonucleic acid; ADA= anti-drug- antibodies.

Appendix 1 Schedule of Assessments: Table C (cont.)

- 1 **Safety Follow-Up:** *Patients who discontinue treatment early for any reason and patients who complete the study treatment period will be followed up for 48 weeks after the last infusion of OCR. When patients begin an alternative treatment for MS (see Section 4.6.3.1 on prohibited therapies), or start commercial OCR, they will be discontinued from the SFU and from the study.*
- 2 **Flow cytometry:** including CD19 and other circulating B-cell subsets, T cells, NK cells, and other leukocytes.
- 3 A **semi-structured telephone interview** will be conducted by site personnel familiar with the patient(s) every 4 weeks (\pm 3 days) between the study visits throughout all periods and the SFU until 48 weeks after the last infusion of OCR. See [Appendix 2](#) for the semi-structured telephone interview.
- 4 Routine safety labs: hematology and chemistry.
- 5 Needs to be assessed only every 24 weeks.
- 6 ADA: two serum samples are required.
- 7 Hepatitis monitoring: hepatitis to be monitored only in patients with screening results of HBsAg negative, HBcAb positive, and HBV DNA negative, inclusive (HBcAb test to be done every 24 weeks).
- 8 A dedicated (scheduled or unscheduled) safety follow-up visit directly prior to the start of an alternative MS treatment is required for patients who begin an alternative treatment for MS while in safety follow-up in order to assess the patient's clinical status and safety parameters.

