4.7.4 Safety Follow-Up

Patients who discontinue treatment early for any reason and patients who complete the study treatment period will be followed up for 48 weeks after the last infusion of OCR. When patients begin an alternative treatment for MS (see Section [4.6.3.1](#) on prohibited therapies), or start treatment with commercial OCR, they will be discontinued from the SFU and from the study. SFU visits will be performed at 12-week intervals.

A dedicated (scheduled or unscheduled) safety follow-up visit directly prior to the start of an alternative MS treatment is required in order to assess the patient's clinical status and safety parameters. Additionally, an MRI scan should be performed within 4 weeks prior to the start of an alternative MS treatment (unless MRI has already been performed within prior 8 weeks; for details on assessments, [Appendix 1](#)).

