4.7.7 Withdrawal Visits

At the moment a patient meets one or more of the withdrawal criteria (Section [4.8.2](#)), the patient will be regarded as withdrawn from treatment. Patients who withdraw from OCR treatment will need to complete all assessments as shown in [Appendix 1](#) and will enter the SFU. Patients in Group B who do not receive an infusion of OCR in the OOE will not enter SFU.

After entering the SFU, if patients begin an alternative treatment for MS (see Section [4.6.3.1](#) on prohibited therapies), or start treatment with commercial OCR, they will be discontinued from the SFU and from the study.

All patients will undergo a complete final evaluation according to the 'Withdrawal from Treatment Visit' in the Schedule of Assessments ([Appendix 1](#)). Thereafter, all patients will be treated according to individual center practice.

For patients who have withdrawn from the Immunization Study Period or the OOE or who are not eligible for treatment with OCR, the investigator should decide on further treatment of the underlying disease.

However, as sufficient data are not available to inform risks associated with switching to other products, certain treatments for MS, such as lymphocyte-depleting agents or lymphocyte-trafficking blockers (alemtuzumab, natalizumab, fingolimod, dimethyl fumarate, cladribine, daclizumab, cyclophosphamide, azathioprine, etc.), are strongly discouraged for as long as the patient remains B-cell depleted because of unknown effects on the immune system (e.g., increased risk, incidence, or severity of infection) (see also Section 4.6.3.1 for recommendations on alternative treatments for MS).

Please note: at the withdrawal from the Immunization Period or the OOE Period for patients in Groups A and B, an MRI scan will be required only if not performed in the prior 4 weeks.

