4.7.9.3 Hepatitis Screening and Liver Function Monitoring

Patients with recurrent or chronic hepatitis B or history/presence of hepatitis C infection must be excluded from enrollment into the study (see Section 4.1.2). In addition, hepatitis B and C serology will be performed at screening. Patients who have a positive result to either HBsAg, or total HBcAb associated with positive viral DNA titers as measured by PCR, or a positive result for HepCAb should be excluded from the trial. Patients with evidence of past resolved hepatitis B infection (i.e., positive total HBcAb associated with a negative viral DNA) can be enrolled, and will have the hepatitis B viral DNA checked regularly as per [Appendix 1](#). Patients in whom the viral DNA becomes positive but in whom the quantity is at the lower limit of detection of the assay should have the test repeated as soon as possible. Patients found to have a confirmed viral DNA-positive test should be referred to a hepatologist for immediate assessment.

These patients will not receive further infusions of OCR and will enter the SFU. Liver function (i.e., ALT/SGPT, AST/SGOT, γ glutamyl transferase, alkaline phosphatase, total bilirubin) should be reviewed throughout the study. Patients who develop evidence of liver dysfunction should be assessed for viral hepatitis and, if necessary, referred to a hepatologist or other appropriately qualified expert. Study drug should be withheld until the diagnosis of viral hepatitis has been excluded. Patients who develop hepatitis B or C should be withdrawn from the study and should enter the SFU. Should treatment be prescribed, this will be recorded in the eCRF. Patients with viral hepatitis due to other agents, such as hepatitis A, may resume treatment after recovery. Please refer also to Section 5.3.5.7 for further guidelines on liver function monitoring.

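### Table C note 7 orders an HBcAb test in safety follow-up where the protocol's monitoring test is HBV DNA

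*Protocol*

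**What the plan says.** Section 4.7.9.3 of the Protocol admits patients with past, resolved hepatitis B: HBcAb positive with negative viral DNA. They "can be enrolled, and will have the hepatitis B viral DNA checked regularly", on the schedule in Appendix 1. The same section says what follows from a result. A positive DNA result at the lower limit of detection is repeated, and "Patients found to have a confirmed viral DNA-positive test should be referred to a hepatologist for immediate assessment". Those patients get no more ocrelizumab and enter safety follow-up.

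Appendix 1 gives the schedule in three tables.

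- **Tables A and B** (immunization and extension periods) each have an HBV DNA row with note 19: "For those eligible patients enrolled with positive total HBcAb, HB virus DNA (PCR) must be repeated every 24 weeks".
- **Table C** (safety follow-up) has an HBV DNA row with note 7. Note 7 restricts monitoring to patients who at screening were HBsAg negative, "HBcAb positive, and HBV DNA negative, inclusive (HBcAb test to be done every 24 weeks").
- The HBV DNA row of Table C has an unannotated x under the heading "Visits every 12 weeks (± 7 days") and another in the end-of-observation column. Four other rows carry note 5 on their 12-weekly x: "Needs to be assessed only every 24 weeks".

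**The concern.** Note 7 selects patients because they are HBcAb positive and then tells the site to test HBcAb. A repeat positive tells the site only what it knew at screening, and the protocol attaches no action to the result. The test that does lead to action, viral DNA, is the label of the row but is missing from the note's instruction.

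The topic is a genuine safety matter. Section 5.1.1.2 reports hepatitis B reactivation in one rheumatoid arthritis patient on ocrelizumab (none in MS patients in interventional studies) and asks that patients with positive serology be monitored to prevent it. Section 4.8.2 makes reactivation a reason to stop treatment. Section 5.1.1.5 gives a median time to B-cell repletion of 72 weeks (range 27 to 175), which is longer than the 48 weeks of follow-up. Table C is thus the schedule for a period in which many patients will still be depleted, and its instruction on this test should be right.

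**Working it through.** The plan states no figure to reproduce. The check is a cross-reading, followed by a count of scheduled tests.

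**Step 1. Which test?** Every place that deals with monitoring HBcAb-positive patients after entry:

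| Place | Test named |
|---|---|
| Section 4.7.9.3, monitoring and action rules | viral DNA |
| Table A, row and note 19 | HBV DNA (PCR) |
| Table B, row and note 19 | HBV DNA (PCR) |
| Table C, row label | HBV DNA |
| Table C, note 7 | HBcAb |

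Only note 7 differs. Table C has no HBcAb row, and in Tables A and B the hepatitis serology row is marked at screening only. Nothing else in the protocol schedules a repeat HBcAb test.

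**Step 2. Which interval?** Note 7 says 24 weeks and note 19 says 24 weeks. The possible counter-evidence is the unannotated x under a 12-weekly heading. Two features of Appendix 1 show that such an x does not fix the interval when the row label carries its own note.

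- In Table C, the telephone follow-up row also has an unannotated x under the 12-weekly heading, yet its label note (note 3) sets calls every 4 weeks.
- In Table A, HBV DNA is marked at Days 1, 85 and 169. The gaps are 85 − 1 = 84 days and 169 − 85 = 84 days, or 12 weeks each. In Table B it is marked at Days 238 and 252, a gap of 14 days. Both rows carry the 24-week note 19.

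Marks closer together than 24 weeks, beside a label note saying 24 weeks, are how this row is written throughout the appendix.

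**Step 3. How many tests?** Inputs: 48 weeks of follow-up after the last infusion (Section 4.7.4 and Table C, note 1); visits every 12 weeks; interval in note 7 of 24 weeks. All counts are upper bounds per monitored patient, with the Week 48 visit counted as the end-of-observation visit. They fall if follow-up is entered late or ends early.

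- Row read alone: 48 / 12 = 4 DNA tests (Weeks 12, 24, 36, 48).
- Note 7 with the test name corrected: 48 / 24 = 2 DNA tests (Weeks 24, 48).
- Row and note both taken literally: 4 DNA tests plus 48 / 24 = 2 HBcAb tests.
- Difference between the first two: 4 − 2 = 2 DNA tests.

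**The case against.** The strongest reply is that this is a slip of the pen that no site would act on. The row says HBV DNA, Section 4.7.9.3 says viral DNA, and samples go to a central laboratory under a manual that is not among these documents. If row and note are both followed literally, no DNA test is lost and two unneeded HBcAb tests are added.

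There are also backstops. Section 4.7.7 says that "Patients who withdraw from OCR treatment will need to complete all assessments as shown in" Appendix 1, and HBV DNA is marked at the withdrawal-from-treatment visit in both Tables A and B. Liver chemistry is drawn at each 12-weekly visit, which is 48 / 12 = 4 draws. Section 4.7.9.3 has liver function reviewed throughout the study and viral hepatitis considered when it is abnormal. Telephone interviews between visits, 48 / 4 − 48 / 12 = 8 of them, ask about signs of infection.

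Most of this stands, and it limits the size of the point. It does not make the instruction correct. The withdrawal-visit test comes before follow-up, and chemistry and interviews are not DNA tests.

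A reader might go further in two ways, and the documents support neither.

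- *That Table C leaves patients without DNA testing.* This requires a site to follow the footnote and disregard the label of the row it annotates, which is marked in both columns.
- *That Table C contradicts itself on the interval, 12 weeks against 24, as a second error.* The absence of note 5 is untidy, but Step 2 shows that a label note can set the interval over an unannotated x. Read literally, note 7 sets an interval for HBcAb only, so it does not conflict with the DNA row. Once the test name is corrected, its 24 weeks agrees with note 19. No note or section text calls for 12-weekly DNA testing.

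**Conclusion.** Note 7 names the wrong test, and this can be said with high confidence because every other statement on monitoring these patients names HBV DNA. The intended interval is recoverable as 24 weeks from notes 7 and 19. Note 19 sits in the tables for the earlier study periods, so this is a reading of Appendix 1 as a whole and not of Table C alone.

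This is a minor correction to a safety schedule. In scheduled tests, its size is the gap between up to 2 DNA tests (24-weekly) and up to 4 (row read alone) per monitored patient over a full 48 weeks. The number of HBcAb-positive patients entering follow-up is not given. It is probably small, and no estimate is made here. Immunology endpoints, sample size and efficacy analyses are unaffected. The conclusion assumes that the laboratory manual, which was not available, does not already override the note.

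**What to change.** In Table C, note 7, replace the words HBcAb test with HBV DNA (PCR) test and keep the 24-week interval, so that the note matches note 19 of Tables A and B. For clarity, add note 5 to the 12-weekly x of the HBV DNA row, as is already done on four other rows.

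The cost is one phrase and one superscript, which can go into the next amendment. No visit or new assay is added, since HBV DNA is already a row of the table. The one downside should be stated openly: the edit confirms up to 2 DNA tests over the 48 weeks, and a site that had been reading the row alone might have been doing up to 4.
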